6 STUDY TREATMENTS

6.1 Description of Treatments and Study Drug and Supplies

Both study drugs will be administered as an open-label IV solution, followed by observation.

Under no circumstances is the investigator allowed to release these clinical supplies for use by another physician not named on Form FDA 1572 (and/or country or region equivalent document) or to administer study drug to a patient who is not enrolled in this study. Study drug must be dispensed at an institution specified on Form FDA 1572 (or equivalent document).

6.1.1 Margetuximab

Margetuximab is a sterile, clear-to-slightly-opalescent, colorless-to-pale-yellow or pale-brown, preservative-free solution for IV administration. Some visible, translucent, proteinaceous, margetuximab particles may be present. Margetuximab is supplied in single-use, 10-mL clear glass vials with FluroTec[®] coated gray butyl rubber serum stoppers and aluminum seals with plastic overseals. Each vial contains 250 mg margetuximab (25 mg/mL) in 10 mL of solution. The product is formulated in a buffer containing 1.1 mg/mL sodium phosphate monobasic, monohydrate, 0.58 mg/mL sodium phosphate dibasic, heptahydrate, 2.9 mg/mL sodium chloride, 11 mg/mL L-arginine hydrochloride, 30 mg/mL sucrose, and 0.1 mg/mL Polysorbate 80, in Sterile Water for Injection, pH 6.1.

6.1.2 Pembrolizumab

Pembrolizumab (marketed as KEYTRUDA[®] by Merck & Co., Inc, Whitehouse Station, NJ 08889 U.S. License No. 0002) is a humanized monoclonal antibody that blocks the interaction between PD-1 and its ligands, PD-L1 and PD-L2. Pembrolizumab is an IgG4 kappa immunoglobulin with an approximate molecular weight of 149 kDa.

Pembrolizumab is supplied as lyophilized powder in a single-use vial for reconstitution or as solution for infusion in single-use vials.

Table 3 Pembrolizumab Product Descriptions

Product Name	Dosage Form and Strength
MK-3475	For Injection: 50 mg lyophilized powder in single-dose vial for reconstitution or Injection: 100 mg/4 mL solution in single-use vial

Pembrolizumab lyophilized powder is a sterile, preservative-free, white to off-white lyophilized powder in single-use vials. Each vial is reconstituted with 2.3 mL Sterile Water for Injection, USP and diluted for IV infusion. Each 2 mL of reconstituted solution contains 50 mg of pembrolizumab and is formulated in L-histidine (3.1 mg), polysorbate 80 (0.4 mg), and sucrose (140 mg). May contain hydrochloric acid/sodium hydroxide to adjust pH to 5.5.

Pembrolizumab solution for infusion is a sterile, non-pyrogenic aqueous solution supplied in a vial containing 100 mg/4 mL of pembrolizumab.

6.2 Drug Preparation

6.2.1 General Guidelines and Precautions

The calculated dose of margetuximab will be administered based on the patient's actual weight at Day 1. Significant ($\geq 10\%$) change in body weight from baseline should prompt recalculation of dose.

Infusion or allergic reactions may occur with the infusion of monoclonal antibodies and other protein-based therapeutics. Precautions for anaphylaxis or infusion-related reactions (including CRS) should be observed during both margetuximab and pembrolizumab administration. Supportive measures may include, but are not limited to: epinephrine, antihistamines, corticosteroids, IV fluids, vasopressors, oxygen, bronchodilators, diphenhydramine, and acetaminophen. Please refer to [Section 6.5.1](#) for specific guidelines regarding the management of infusion reactions. Supportive care measures consistent with optimal patient care will be provided throughout the study according to institutional standards.

Separate infusion bags must be used for each infusion. Pembrolizumab is to be administered first.

An effort should be made to begin the margetuximab infusion within 30 minutes after the completion of the pembrolizumab infusion. It is understood that this window may not always be attainable, but is the preferred window of time to administer margetuximab.

6.2.2 Pembrolizumab Preparation

The Pharmacy Manual contains specific instructions for the preparation of the pembrolizumab infusion and administration of infusion solution.

6.2.3 Margetuximab Preparation

The Pharmacy Manual contains specific instructions for the preparation of the margetuximab infusion and administration of infusion solution.

6.2.4 Placebo or Control

There will be neither placebo nor active control drug for this study.

6.3 Study Drug Administration

Note: Dosing interruptions are permitted in the case of medical/surgical events or logistical reasons (i.e. elective surgery, unrelated medical events, patient vacation, holidays, etc.) not related to study therapy.

6.3.1 Pembrolizumab Administration

The pembrolizumab infusion solution should be administered over 30 minutes through an IV line containing a sterile, non-pyrogenic, low-protein binding 0.2 micron to 5 micron in-line or add-on filter using an infusion pump. Do not co-administer other drugs through the same infusion line.

6.3.2 Margetuximab Administration

After pembrolizumab administration, margetuximab will be administered as a 120-minute (2-hour) IV infusion using a sterile PES 0.2 micron filtered administration set. *Margetuximab should not be administered as an IV push or bolus.*

Margetuximab should not be mixed or diluted with other drugs.

6.4 Selection and Timing of Dose for Each Patient

Patients will be assigned to successive dose cohorts as described in [Section 4.1.2](#) and [Section 4.1.3](#). On each treatment day, pembrolizumab will be administered first, followed by margetuximab administration within 30 to 120 minutes following completion of pembrolizumab infusion.

6.5 Potential Adverse Events and Supportive Care Measures

6.5.1 Infusion-Related Reactions Including Cytokine Release Syndrome

Infusion reactions (including cytokine release syndrome [CRS]) associated with either margetuximab or pembrolizumab administration should be managed according to the standard practice of medicine. General guidelines for the management of such reactions are provided in this section. However, severe reactions may require more intensive interventions (e.g., steroids, anti-TNF α antibodies, and/or IL-6 inhibitors).

Patients should be monitored closely for the development of infusion-related reactions during the pembrolizumab and margetuximab infusions. Medications and supportive measures for the treatment of severe hypersensitivity reactions should be available for immediate use for an infusion reaction during study drug administration and may include, but are not limited to: subcutaneous (SC) epinephrine (0.3 to 0.5 mL of a 1:1000 solution), antihistamines (e.g., diphenhydramine 25 to 50 mg IV), corticosteroids (e.g., dexamethasone 20 mg IV push or equivalent), IV fluids, vasopressors, oxygen, bronchodilators, and antipyretics. Resuscitation equipment and other supplies for the emergency management of an allergic/toxic reaction must be available. The patient should be treated according to the best available local practices and procedures. All supportive measures consistent with optimal patient care will be provided throughout the study according to institutional standards.

Should symptoms of fever or chills develop it may be difficult to distinguish among potential causes of the symptoms including emerging infection, or infusion reaction. Patients should be evaluated carefully for the presence of infection, with the acquisition of cultures and/or implementation of empiric antibiotic therapy as appropriate based on the assessment of the

investigator. Please refer to [Section 6.5.1.3](#) for guidance regarding the management of infusion reactions.

If a patient has a Grade 1 or 2 infusion reaction with pembrolizumab and the investigator considers it prudent, based on medical judgment, for a delay of the patient's margetuximab drug administration at the scheduled infusion time, the margetuximab dose may be administered on the following day (the day after the pembrolizumab infusion). For Grade 3 infusion reactions with pembrolizumab that resolve completely or to Grade 1 within 12 hours, the scheduled dose of margetuximab may be administered the following day with premedications as listed below.

6.5.1.1 Grading of Infusion Reactions

Infusion reactions will be categorized as follows:

- Grade 1: mild reaction; infusion interruption not indicated, intervention not indicated; Note: although interruption in infusion is not indicated, temporary rate reduction indicated before resuming original rate, as patient tolerates (see [Section 6.5.1.3](#));
- Grade 2: therapy or infusion interruption indicated but responds promptly to symptomatic treatment [e.g., antihistamines, non-steroidal anti-inflammatory drugs (NSAIDs), narcotics, IV fluids]; prophylactic medications indicated for ≤ 24 hours;
- Grade 3: prolonged (e.g., not rapidly responsive to medication and/or brief interruption of infusion); recurrence of symptoms following initial improvement; hospitalization indicated for clinical sequelae (e.g., renal impairment, pulmonary infiltrates);
- Grade 4: life-threatening consequences; pressor or ventilatory support indicated;
- Grade 5: death.

The above grading scale is the CTCAE v 4.03 grading scale for infusion reaction, which is nearly identical to the CTCAE v 4.03 grading scale for cytokine release syndrome and allergic reaction, and therefore considered appropriate for grading all infusion reactions in this study, irrespective of the underlying mechanism of the reaction. The Sponsor's Medical Monitor or designee should be contacted immediately if questions arise concerning the grade of the reaction.

6.5.1.2 Premedications and Prophylaxis

Premedication should be administered per institutional standards and investigator's criterion. The following are suggested guidelines for the investigator regarding prophylactic pre-infusion measures to be followed to mitigate the occurrence or severity of potential infusion reactions.

Prior to first infusion of pembrolizumab (Cycle 1, guidelines to be followed):

- Acetaminophen 650-1000 mg orally (PO) or ibuprofen 400 mg PO
- Diphenhydramine 50 mg PO or IV or equivalent H1 antagonist

- Ranitidine 300 mg PO or IV or equivalent H2 antagonist
- Dexamethasone 20 mg IV

Only one dose of pre-infusion prophylaxis steroids administered prior to pembrolizumab may be required. Non-steroidal pre-medications may be administered prior to the subsequent margetuximab infusion if warranted.

If prophylaxis was used prior to pembrolizumab infusion, no steroidal prophylaxis is needed prior to margetuximab infusion; non-steroidal prophylaxis may be employed per clinical discretion of the investigator.

For all subsequent administrations of pembrolizumab and margetuximab, patients who had infusion reactions who were not adequately or only moderately controlled with acetaminophen, diphenhydramine, or ranitidine, IV dexamethasone at doses of 4 mg may be considered.

6.5.1.3 Management of Observed Infusion Reactions

The following are treatment guidelines (which may be modified as needed by the investigator according to the best practices of medicine) for infusion reactions. Note that these apply to both margetuximab and pembrolizumab:

- Grade 1:
 - Slow the infusion rate by 50%.
 - Monitor the patient for worsening of condition.
 - Continue rate at 50% reduction and increase dose rate to the original rate by doubling the infusion rate after 30 minutes, as tolerated to the initial rate. Consideration can be given to beginning all subsequent infusions at 50% rate and increasing as tolerated.
 - If a patient has an infusion reaction with pembrolizumab, the margetuximab infusion can be given (without prophylactic medications) on the same day if the infusion reaction resolves within 3 hours. For scheduling purposes, the margetuximab infusion may be given the next day if the reaction lasts greater than 3 hours.
 - If a patient has an infusion reaction with pembrolizumab, prophylactic preinfusion medications should be given prior to all subsequent pembrolizumab infusions as written below for Grade 1 infusion reactions.
 - If a patient has an infusion reaction with margetuximab, prophylactic preinfusion medications should be given prior to all subsequent margetuximab infusions as written below.

- The following prophylactic preinfusion medications are recommended prior to future infusions of margetuximab and/or pembrolizumab for patients who experience Grade 1 infusion reactions: diphenhydramine 50 mg PO or IV (or equivalent) and/or acetaminophen 650 mg PO at least 30 minutes before additional study drug administrations.
- Report as an Adverse Event of Special Interest (AESI) by completing the appropriate eCRF page.

- Grade 2:
 - Stop the infusion.
 - Administer diphenhydramine hydrochloride 25-50 mg IV, acetaminophen 650 mg PO for fever, and oxygen and bronchodilators for mild bronchospasm.
 - Resume the infusion at 50% of the prior rate once the infusion reaction has resolved or decreased to Grade 1. The rate may then be escalated to the original rate after 30 minutes, as tolerated. Consideration can be given to beginning all subsequent infusions at 50% rate and increasing as tolerated.
 - Monitor for worsening condition. If symptoms recur, discontinue the infusion; no further study drug will be administered at that visit.
 - If a patient has an infusion reaction with pembrolizumab:
 - The margetuximab infusion can be administered on the same day if the infusion reaction resolves within 3 hours. The margetuximab infusion may be given the next day if the infusion reaction last longer than 3 hours.
 - Premedication of diphenhydramine hydrochloride 25-50 mg IV and acetaminophen 650 mg PO should be administered 30 minutes prior to the margetuximab dose. If no corticosteroids were given for the pembrolizumab infusion reaction, dexamethasone 20 mg IV may be considered prior to margetuximab administration.
 - Prophylactic pre-infusion medications should be given prior to all subsequent pembrolizumab infusions. Patients who experience a Grade 2 infusion reaction should be pre-medicated with diphenhydramine hydrochloride 25-50 mg IV and acetaminophen 650 mg PO for subsequent doses of pembrolizumab.
 - If a patient has an infusion reaction with margetuximab, prophylactic pre-infusion medications should be given prior to all subsequent margetuximab infusions.

- For patients with Grade 2 infusion reactions despite premedication with diphenhydramine and acetaminophen, corticosteroids (dexamethasone 20 mg IV) should be considered for acute management of the event and should be added to the premedication regimen for subsequent dosing of pembrolizumab and /or margetuximab.
- Report as an Adverse Event of Special Interest by completing the appropriate eCRF page.

- Grade 3:
 - STOP THE INFUSION AND DISCONNECT THE INFUSION TUBING FROM THE PATIENT.
 - TO AVOID EXACERBATION OF INFUSION REACTION OR CRS: DO NOT FLUSH THE TUBING – ASPIRATE RESIDUAL DRUG FROM THE PORT LUMEN.
 - Administer diphenhydramine hydrochloride 25-50 mg IV, dexamethasone 20 mg IV (or equivalent), and other medications/treatment as medically indicated. Higher doses of corticosteroids (e.g. methylprednisolone 2-4 mg/kg IV or the equivalent) may also be considered for acute management.
 - IV fluids, supplemental oxygen and bronchodilators should be considered as appropriate.
 - **Grade 3 infusion reaction:** If the Grade 3 infusion reaction occurs with pembrolizumab, both margetuximab and pembrolizumab will be discontinued for that day. If symptoms have resolved to baseline within 12 hours, margetuximab may be infused the next day. Pembrolizumab would be re-challenged at the next scheduled infusion cycle, with a 50% reduction of infusion rate. In addition, patients should be pre-medicated for this re-challenge and for any subsequent doses of pembrolizumab with the following: diphenhydramine hydrochloride 25-50 mg IV, oral acetaminophen 625 mg and dexamethasone 20 mg IV. Margetuximab dosing can be resumed with at the next scheduled infusion day if the pembrolizumab Grade 3 infusion reaction resolved to grade 1 within 12 hours. Patients who have a Grade 3 infusion reaction that does not resolve within 12 hours despite medical management should not receive further margetuximab or pembrolizumab treatment.
 - Patients who experience a second Grade 3 infusion reaction at the time of re-challenge of margetuximab or pembrolizumab (irrespective of duration of first Grade 3 reaction) will permanently discontinue margetuximab and pembrolizumab.
 - Report as an Adverse Event of Special Interest and an Immediately Reportable Event (IRE) within 24 hours.
 - Report the event as a SAE, if appropriate.

- Grade 4:
 - STOP THE INFUSION AND DISCONNECT THE INFUSION TUBING FROM THE PATIENT.
 - TO AVOID EXACERBATION OF INFUSION REACTION OR CRS: DO NOT FLUSH THE TUBING.
 - Administer diphenhydramine hydrochloride 50 mg IV, methylprednisolone 2-4 mg/kg IV (or more as considered appropriate), and other medications/treatment as medically indicated (e.g., an IL-6 receptor inhibitor or IL-6 inhibitor, an IL-2 receptor inhibitor, and/or an anti-TNF α antibody).
 - Give epinephrine or bronchodilators as indicated.
 - Support ventilation and blood pressure as indicated.
 - Report as an Adverse Event of Special Interest and an IRE within 24 hours.
 - Report the event as an SAE.
 - Patients who have a Grade 4 infusion reaction will not receive further margetuximab or pembrolizumab.

- Grade 5:
 - Report as an IRE within 24 hours.
 - Report the event as an SAE.

All changes in the infusion of either margetuximab or pembrolizumab, including interruption of the infusion and its duration as well as reductions in infusion rate and duration, must be recorded.

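### For a Grade 3 pembrolizumab infusion reaction down to Grade 1 but not baseline within 12 hours, Protocol 6.5.1 and 6.5.1.3 conflict on when margetuximab may be given, and 6.5.1.3 leaves 'resolve' undefined in its stop sentence

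*Protocol*

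**What the plan says.** Two places in the Protocol govern margetuximab after a Grade 3 reaction to pembrolizumab.

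- **Section 6.5.1, closing paragraph.** For Grade 3 pembrolizumab reactions "that resolve completely or to Grade 1 within 12 hours, the scheduled dose of margetuximab may be administered the following day", with premedication.
- **Section 6.5.1.3, Grade 3 bullet.** Both drugs are withheld for the rest of that day. Then come four statements:
  - On next-day dosing: "If symptoms have resolved to baseline within 12 hours, margetuximab may be infused the next day".
  - On pembrolizumab: "Pembrolizumab would be re-challenged at the next scheduled infusion cycle, with a 50% reduction of infusion rate". No resolution level is attached to this sentence.
  - On later margetuximab dosing, which "can be resumed with at the next scheduled infusion day if the pembrolizumab Grade 3 infusion reaction resolved to grade 1 within 12 hours".
  - On stopping: a Grade 3 reaction "that does not resolve within 12 hours despite medical management should not receive further margetuximab or pembrolizumab treatment".

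Section 6.5.1.3 opens by describing its content as treatment guidelines that the investigator may adapt to best medical practice. It also stops both drugs permanently if a second Grade 3 reaction occurs on re-challenge.

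**The concern.** The two sections use the same 12-hour clock but different resolution levels. Section 6.5.1 puts complete resolution and Grade 1 together and allows next-day margetuximab for both. Section 6.5.1.3 separates them, with baseline leading to the next day and Grade 1 to the next scheduled infusion day. A patient at Grade 1 at 12 hours falls exactly where they differ.

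What is at stake is when a patient with residual symptoms after a severe reaction receives a second antibody. The Protocol synopsis plans for approximately 29 institutions, and safety and tolerability are part of a primary objective (Protocol 3.1). Sites could manage identical patients differently, each following the text of one section.

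The stop sentence adds a separate difficulty. It turns on whether the reaction has resolved within 12 hours, and it does not state the level that counts as resolved.

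**Working it through.** The plan gives no figure to reproduce, and no power, sample size or event count is involved. The check applies each instruction to the possible patient states at 12 hours after a Grade 3 pembrolizumab reaction.

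| State within 12 hours | Protocol 6.5.1 | Protocol 6.5.1.3 |
|---|---|---|
| Back to baseline | Margetuximab permitted next day | Margetuximab permitted next day |
| Grade 1, not baseline | Margetuximab permitted next day, with premedication | Next-day condition not met; margetuximab can resume at the next scheduled infusion day |
| Still above Grade 1 | Next-day permission does not apply | No further margetuximab or pembrolizumab |

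The sections agree in the top and bottom rows and conflict in the middle row.

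**Size of the timing difference.** A cycle is 3 weeks with both drugs on Day 1 (Protocol 4.1.1), so the next scheduled infusion day is 3 × 7 = 21 days after the reaction. With the ±3-day visit window in Appendices 1 and 2, that is 21 − 3 = 18 to 21 + 3 = 24 days. Section 6.5.1 gives 1 day. The nominal difference is 21 − 1 = 20 days, which amounts to whether that cycle's margetuximab dose is given.

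**Can the sentences of 6.5.1.3 be read together?** Yes. Baseline and Grade 1 work as two tiers with two timings, so 6.5.1.3 does not contradict itself on this point. That reading sharpens the conflict with 6.5.1, which merges the same two tiers.

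**What does *resolve* mean in the stop sentence?** The Protocol's own usage points both ways.

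- Towards Grade 1 counting as resolved: 6.5.1 treats reaching Grade 1 as one way of resolving. The sentence just before the stop sentence in 6.5.1.3 does the same and lets margetuximab resume. Section 4.5.1 (Dose Delays) also speaks of toxicity resolving to Grade 1 or lower, though it refers infusion reactions to 6.5.
- Towards Grade 1 not counting: the Grade 2 bullet of 6.5.1.3 lists being resolved and falling to Grade 1 as alternatives. Section 7.9.5 defines resolution, for follow-up of serious adverse events, as return to pre-treatment status or a stable condition expected to remain chronic.
- No help either way: the dose-limiting toxicity exception in 4.2.3 counts how long the Grade 3 reaction lasts (under 12 hours) and does not mention baseline.

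If *resolve* meant return to baseline, the stop sentence would cancel the Grade 1 resumption sentence immediately before it. The text therefore leans against that reading without excluding it.

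**The case against.** The strongest reply is that the wording is permissive. Margetuximab *may* be given the next day and *can* be resumed at the next scheduled day, and 6.5.1.3 says neither that baseline is the only route to next-day dosing nor that Grade 1 must wait. The section is also adaptable guidance. On this view 6.5.1 widens the options and nothing is contradicted.

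Part of this stands. The exclusive reading of the baseline condition is an inference, although the natural one, and investigator discretion softens the practical effect. The reply does not remove the conflict. If Grade 1 already permits next-day dosing, the baseline condition in 6.5.1.3 does no work. Discretion also needs one default to depart from, and here the default depends on the section consulted.

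A reader might infer two stronger claims, and the documents support neither.

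- *Three incompatible instructions, the third being permanent discontinuation.* This needs *resolve* to mean return to baseline, which the stop sentence does not say and which would defeat the sentence before it. It is an undefined term.
- *Distorted summaries of adverse events of special interest.* Protocol 7.9.3 puts every infusion reaction in that category whatever dosing follows, and SAP 6.7.1 counts patients with at least one event. The index reaction already places the patient in the table.

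**Conclusion.** The point holds as one two-way conflict plus one undefined term. For a Grade 3 pembrolizumab reaction at Grade 1 but not baseline within 12 hours, 6.5.1 permits margetuximab after 1 day and 6.5.1.3 places it at about 21 days. Whether residual Grade 1 could trigger the permanent stop is unclear from the stop sentence alone.

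The conclusion assumes that the baseline condition in 6.5.1.3 is meant as a condition and that the next scheduled infusion day is Day 1 of the following cycle. The documents give no frequency for this patient state, so the number of patients affected cannot be stated. No sample size, response or survival analysis depends on it. An effect on summaries of drug withdrawal would rest largely on the doubtful permanent-stop reading. The matter should be corrected because it bears on patient safety and on uniform conduct across sites.

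**What to change.** Reconcile Protocol 6.5.1 and 6.5.1.3 so that, after a Grade 3 pembrolizumab reaction, one resolution level and one timing apply to margetuximab in both places. In the sentence of 6.5.1.3 that stops both drugs, state whether a reaction at Grade 1 within 12 hours counts as resolved. Which level and timing to adopt is a clinical decision for the sponsor, and this review takes no view on it.

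The cost is a protocol clarification confined to these two sections, with notice to sites. The SAP needs no change.
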